6. STUDY POPULATION

6.1. Safety Population

For analyses of ocular adverse events (AEs) and safety parameters assessed per eye, the Safety population will consist of all study eyes which received at least one administration of investigational product (IP) and study eyes will be classified by the actual treatment received. For analyses of non-ocular AEs and safety parameters assessed per subject, the Safety population will consist of all subjects which received at least one administration of IP and subjects will be classified by the actual treatment received.

6.2. Full Analysis Set

The Full Analysis Set (FAS) will consist of all study eyes that are randomized and received at least one administration of study treatment. The efficacy analyses will be performed using the FAS and study eyes will be classified by the randomized treatment assignment, irrespective of the actual treatment received. For analyses of other parameters assessed per subject, the FAS population will consist of all subjects whose study eye(s) are randomized and received at least one IP administration and subjects will be classified by the planned treatment assignment.

6.3. **Per-Protocol Population**

The Per-Protocol (PP) Population will be a subset of the FAS population. The PP population will be the analysis population for sensitivity analyses and will use treatment as randomized. Any study eye affected by a significant protocol deviation (such that the outcome to treatment could be altered) will be excluded from the PP Population. In addition, any study eye without the Month 5 VH score will be excluded from the PP Population.

Before database lock and the unmasking of treatment assignments, Santen's study team will review all protocol deviations, identify study eyes with any protocol deviation that could impact the efficacy outcome, and determine whether or not to exclude the study eye from the PP population.

When data are presented at the subject level, PP Population is referred to subjects who have all of their study eyes qualified for the PP Population.

6.4. Intent-to-Taper Population

The Intent-to-Taper population will be a subset of the FAS population, consisting of study eyes from subjects who were taking systemic (oral) corticosteroids at a stable prednisone-equivalent dose between \geq 15 mg/day and \leq 40 mg/day for at least 1 week (7 days) prior to and including on Day 1. The Intent-to-Taper population will be used for the analysis of tapering success performed using eyes as randomized.

When data are presented at the subject level, Intent-to-Taper Population is also referred to subjects who have their study eye(s) qualified for the Intent-to-Taper Population.

6.5. Macular Edema Population

The Macular Edema population will be a subset of the FAS population and will consist of study eyes with central subfield thickness (CST) \geq 300 microns at baseline. It will be the analysis population for the analysis of CST 50-micron response to be performed with study eyes classified by randomized treatment assignments.

When data are presented at the subject level, Macular Edema Population is also referred to subjects who have at least one of their study eyes qualified for the Macular Edema Population.

6.6. Vision 20/40 or Worse Population

The Vision 20/40 or Worse population will be a subset of the FAS population and will consist of study eyes with $BCVA \le 70$ ETDRS letters (Snellen equivalent of 20/40 or worse) at baseline. It will be the analysis population for the analysis of BCVA 3-line response to be performed with study eye classified by randomized treatment assignments.

When data are presented at the subject level, Vision 20/40 or Worse Population is also referred to subjects who have at least one of their study eyes qualified for the Vision 20/40 or Worse Population.

6.7. Open-Label Safety Population

The Open-Label Safety population will include all Safety subjects who received at least one open-label injection of the DE-109 440 μ g. It will be the analysis population for safety analyses for the Open-Label analysis period to be performed with subjects as treated.

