2.1.2.2. Safety Objective

To evaluate the safety of intravitreal injection of DE-109 440 μ g every 2 months for up to one year of dosing for the treatment of active, non-infectious uveitis of the posterior segment of the eye.

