Subjects completing the Month 6 pre-dose evaluations (the final evaluations in the doublemasked period) will begin the open-label period of the study, in which all subjects will receive intravitreal injection of DE-109 440 μ g in the study eye(s) every 2 months for an additional 6 months of dosing (i.e., investigational product (IP) injections at Month 6, Month 8, and Month 10 with a final follow-up evaluation at Month 12). The same study eye(s) treated during the double-masked period will be treated during the open-label period. The open-label period of the study will allow evaluation of the long-term (> 6 months and up to one year) efficacy and safety of DE-109 440 μ g every 2 months in subjects with NIU-PS.

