7. SUMMARY OF STUDY POPULATION DATA

7.1. Subject and Study Eye Disposition

The subject and study eye disposition of FAS population will be summarized by treatment period (double-masked and open-label) and by planned treatment assignments (for double-masked period) and overall.

The FAS and the FAS subsets including the PP Population, Intent-to-Taper Population, Vision 20/40 or Worse Population, and Macular Edema Population, Safety Population, subjects who were taking systemic corticosteroid at baseline, and subjects who completed vitreous haze (VH) assessment at Month 3, Month 5, Month 6, and Month 12 will be tabulated at the subject level. In addition, subjects who discontinued the study before Month 3, Month 5, Month 6, and Month 12 will be tabulated separately by the primary discontinuation reason. Subjects whose study eye(s) are in the FAS will also be summarized by country.

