7.8. Treatment Exposure

The treatment exposure to DE-109 will be reflected by the number of injections received. The treatment exposure to Sham will be the number of administered Sham procedures. For the Double-Masked analysis period, Safety Population study eyes will be tabulated by the number of injections (1, 2, and 3) for each actual Double-Masked treatment and overall. The numbers of injections received during the Double-Masked, Open-Label, and the Entire Study analysis periods will also be listed for the Safety Population.

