Physical examination: Height, weight	The physical exam result was determined as Normal, Abnormal, or No Change. The weight and the height were recorded with one decimal point in inch/cm and lb/kg, respectively. The conversion rules "1 lb = 0.453592 kg" and "1 in = 2.54 cm" will be followed to convert lb to kg and into cm, respectively.
Vital signs: Oral temperature, systolic and diastolic blood pressure, heart rate	The oral temperature was recorded in °F or °C. The conversion rule "°C = $5/9 \times (°F - 32)$ " will be followed to convert °F to °C. The blood pressure (systolic and diastolic) and the heart rate were recorded in mmHg and beats per minute (bpm), respectively.
Laboratory tests: Blood chemistry/hematology, urinalysis	The minimum blood and urine parameters collected in the study are listed in Appendix B. Hematology, chemistry, and urinalysis outcomes were determined by the Clinical Investigator as Normal, Not Clinically Significant Abnormality or Clinically Significant Abnormality based on the
	comprehensive review of the relevant laboratory test results.

 Table 3:
 Safety Assessments (Continued)

The safety-related measures collected in this study include AEs, events of special interest (ESIs), slit-lamp biomicroscopy findings, IOP, best-corrected visual acuity, indirect ophthalmoscopy findings, central subfield thickness, physical exam results, vital signs, and laboratory test results. The Safety population will be used for all summaries.

All the safety-related measures will be summarized descriptively by actual treatment received. Except AEs, the descriptive summary of each ocular safety-related measurement and the change from baseline in that measure will be performed for study eyes and fellow eyes separately.

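### Read literally, the SAP puts all open-label subjects in one 440 µg safety group, and no specified summary isolates safety under up to one year of 440 µg dosing

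*SAP*

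**What the plan says.** The safety objective in SAP 2.1.2.2 concerns 440 µg "every 2 months for up to one year of dosing". In the open-label period all subjects receive the same regimen, with "injections at Month 6, Month 8, and Month 10 with a final follow-up evaluation at Month 12" (SAP 3.1).

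The Open-Label Safety population "will include all Safety subjects who received at least one open-label injection" of 440 µg (SAP 6.7), whatever the masked-phase arm. The grouping rule in 6.7 is: "It will be the analysis population for safety analyses for the Open-Label analysis period to be performed with subjects as treated". SAP 9.1.2 gives the same rule for safety in general: "All the safety-related measures will be summarized descriptively by actual treatment received".

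SAP 9.2 sets AE columns by actual treatment plus a total-drug column, defined as the 440 µg and fixed-dose arms combined. It names no period. SAP 9.1.1 mentions AE tabulations for the Double-Masked and Open-Label periods. SAP 4.4 also defines an Entire Study period, but no AE table is assigned to it.

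On exposure, SAP 7.8 tabulates one, two or three injections for the masked period only. For the longer periods: "The numbers of injections received during the Double-Masked, Open-Label, and the Entire Study analysis periods will also be listed".

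**The concern.** The objective is about one regimen kept up for as long as a year. In the open-label period, treatment received no longer distinguishes anyone, although the subjects have three different histories. If a harm grows with repeated dosing, newly exposed former sham subjects dilute it. If a harm belongs to the first injections, it reappears in the open-label table and can be taken for a long-term effect.

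This matters for the events the SAP singles out in 9.1.1.5, such as cataract, raised IOP, endophthalmitis and drug depot in the visual axis, if any of them depends on cumulative exposure. Prior dose may matter too: Protocol 2.3 reports that non-infectious endophthalmitis was seen mostly at 880 µg, and the dummy dose lies somewhere between 44 and 880 µg.

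Change scores are affected as well. Baseline is the last value before the first IP administration (SAP 8.1.2), and sham counts as IP (SAP 4.1). A former sham eye's change from baseline in IOP at Months 7 to 12 therefore includes six months on sham.

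**Working it through.** **The plan's own figure.** SAP 3.3 gives 80 subjects per arm for 30% versus 12%, 80% power, two-sided α = 0.05, Pearson chi-square. The two-proportion formula with pooled variance and no continuity correction returns 80 per arm, with 80.4% power. The arm sizes used below are therefore sound.

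**Composition of the open-label group.** Inputs: about 200 subjects, 2:2:1 (SAP 3.1 and 3.2). Assumption: full retention, since the documents give no dropout figure.

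| Masked-phase arm | Subjects | Share | DE-109 injections during open label |
|---|---|---|---|
| 440 µg | 200 × 2/5 = 80 | 40% | 4 to 6, all at 440 µg |
| Sham | 200 × 2/5 = 80 | 40% | 1 to 3 |
| Dummy | 200 × 1/5 = 40 | 20% | 4 to 6, the first three at an undisclosed dose |

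So 80/200 = 40% can have a year of 440 µg, and (80 + 40)/200 = 60% can have a year of DE-109 at some dose. If the interim re-assessment adds the maximum of 100 subjects, the counts are 120/120/60 and the shares are unchanged. If retention differs between former sham subjects and the others (70% against 90%, either way round; assumed), the former sham share runs from 34% to 46%.

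**Dilution.** The documents give no event rates by injection number, so all rates here are assumed. Let r₁ be the rate on first injections and r₂ the rate on later ones.

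- Former dummy eyes behave like later injections: pooled = 0.4·r₁ + 0.6·r₂.
- Former dummy eyes behave like first exposure to 440 µg: pooled = 0.6·r₁ + 0.4·r₂.

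| r₁ | r₂ | Dummy as later | Dummy as first |
|---|---|---|---|
| 4% | 12% | 8.8% | 7.2% |
| 5% | 5% | 5% | 5% |
| 5% | 10% | 8% | 7% |
| 5% | 15% | 11% | 9% |
| 5% | 20% | 14% | 11% |
| 15% | 5% | 9% | 11% |

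In the first row, 8.8/12 = 0.73 and 7.2/12 = 0.60, so the later-injection rate is understated by 27% to 40%. In the last row the direction reverses: a true later rate of 5% would be shown as 9% to 11%. With equal rates nothing is distorted. These shares count subjects; applying them to a rate per eye assumes a similar mix of one-eye and two-eye subjects in each arm.

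**Apparent precision.** For an event never seen, the one-sided 95% upper bound is 1 − 0.05^(1/n). With n = 200 it is 1.5%; with n = 80 it is 3.7%. At 70% retention (assumed) the bounds are 2.1% (n = 140) and 5.2% (n = 56). The pooled denominator makes the evidence on a year of 440 µg look firmer than it is.

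**The case against.** Grouping by treatment received is the usual contrast to grouping as randomised, and Protocol 9 uses it that way. It settles where a mis-dosed eye belongs; it does not say that the earlier arm is dropped. The total-drug definition in SAP 9.2 also suggests columns based on the masked-phase arms. If the Safety population keeps that classification, the by-visit summaries in SAP 9.3 to 9.6 would show former 440 µg eyes through Month 12. This reading is possible and stands as an ambiguity, but it is not stated. Carried into the open-label period, it would also leave former sham subjects out of total drug while they are receiving 440 µg. Elsewhere the SAP names the masked-phase treatment explicitly when it wants that grouping (7.7 and 7.8); 6.7 and 9 do not.

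Three stronger readings are tempting and are not supported:

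- A reader might infer that pooling is a stated rule. It is only the literal consequence of the wording. The disposition text in SAP 7.1, "by planned treatment assignments (for double-masked period) and overall", concerns the FAS and is indirect evidence for safety tables.
- A reader might infer that the safety objective goes unanswered. The objective is descriptive and covers any duration up to a year; no safety testing is planned. Masked-period tables, open-label tables and listings of AEs, ESIs and injection counts all give information on it.
- A reader might infer that no planned table can show Months 6 to 12 for the 440 µg arm. The by-visit summaries may do so; the text leaves it open.

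**Conclusion.** The point holds as a gap in specification. On the literal reading open-label safety is one mixed group, and on either reading no AE or ESI summary isolating up to one year of 440 µg is specified. At planned sizes and full retention, 40% of that group can have the exposure the objective describes. The understatement of 27% to 40% rests on assumed rates of 12% and 4%, with the range set by how former dummy eyes behave. It is zero if risk does not depend on injection number.

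This is a cheap improvement to table layout. It has no bearing on alpha, power, sample size or the primary result, and it is not a matter of clinical management.

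**What to change.** - In SAP 6.7 and 9, tabulate open-label safety by masked-phase sequence (440 to 440, sham to 440, dummy to 440) plus total, and say in 9.2 what total drug means in that period.
- Add an Entire Study AE and ESI table, starting at Day 1, for all subjects treated with 440 µg from Day 1. Include those who left before Month 6. Base the description of safety for up to one year on this table. The 440-to-440 open-label column cannot serve alone, because it contains only subjects who reached an open-label injection and so misses anyone who left earlier because of an AE.
- In SAP 7.8, tabulate exposure by number of DE-109 injections, from 1 to 6.
- Optionally, for former sham eyes, also show change from the last value before the first open-label injection.

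The cost is extra columns with smaller denominators (about 80, 80 and 40 subjects) and one extra AE/ESI table. No new data are needed, and the pooled total is kept.

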7. SUMMARY OF STUDY POPULATION DATA

7.1. Subject and Study Eye Disposition

The subject and study eye disposition of FAS population will be summarized by treatment period (double-masked and open-label) and by planned treatment assignments (for double-masked period) and overall.

The FAS and the FAS subsets including the PP Population, Intent-to-Taper Population, Vision 20/40 or Worse Population, and Macular Edema Population, Safety Population, subjects who were taking systemic corticosteroid at baseline, and subjects who completed vitreous haze (VH) assessment at Month 3, Month 5, Month 6, and Month 12 will be tabulated at the subject level. In addition, subjects who discontinued the study before Month 3, Month 5, Month 6, and Month 12 will be tabulated separately by the primary discontinuation reason. Subjects whose study eye(s) are in the FAS will also be summarized by country.

7.2. Demographics and Baseline Characteristics

Subject demographics and subject-level baseline characteristics will be descriptively summarized for FAS population. Specifically, the following variables will be summarized:

- Age at randomization (continuous and categorical: < 65 years or ≥ 65 years)
- Sex (categorical: Male or Female)
- Ethnicity (categorical: Hispanic/Latino or Not)
- Race (categorical: American Indian or Alaska Native, Asian, Black or African American, Native Hawaiian or Other Pacific Islander, White, or Other)
- Study eye (categorical: OD, OS, or OU)
- Laterality of uveitis (bilateral or unilateral)
- Overall prednisone-equivalent dose (mg/day) for subjects whose study eye(s) are in the Intent-to-Taper population

Baseline characteristics will also be descriptively summarized for eye-level FAS by number of enrolled eyes. The following variables will be summarized:

- Baseline VH score for the study eye and the fellow eye
- Anatomic location of uveitis of the study eye (intermediate, posterior, intermediate + posterior, or panuveitis)
- Etiology of uveitis of the study eye
- Duration of uveitis of the study eye in months derived as [Day 1 Visit Date Uveitis Onset Date (observed or imputed)]/30. Partially missing uveitis onset dates, if any, will be imputed using the approach specified in Section 5.2.3.
- Baseline BCVA of the study eye for
 - FAS population

- Vision 20/40 or Worse population
- Baseline CST of the study eye for
 - FAS population
 - Macular Edema population

Other baseline characteristic variables may be summarized as suggested by the data.

7.3. Medical and Surgical History

For this study, medical history (i.e., medical events) will be coded using MedDRA 23.1, 2020 and summarized for the FAS population. Each medical event will be classified into a system organ class (SOC) and mapped to a preferred term (PT).

Subjects reporting any medical history events will be tabulated by SOC and preferred term specified in MedDRA for each planned double-masked treatment assignment and overall. In addition, subjects reporting any medical history events ongoing at baseline, any medical history events in study eyes that are linked to SOC *Eye disorders*, and any medical history events ongoing at baseline in study eyes that are linked to SOC *Eye disorders* will also be tabulated. Any subject with more than one medical and/or surgical term within the same SOC (or mapped to the same preferred term) will be counted only once for that SOC (or preferred term).

7.4. **Protocol Deviations**

In this study, protocol deviations are categorized as follows:

- Informed Consent
- Inclusion/Exclusion Criteria
- Study Drug
- Protocol Procedures/Safety
- Endpoint Data
- Visit Window
- Prohibited Med/Procedures
- Other

A protocol deviation is considered significant if it may affect the subject's rights, safety, or well-being, and/or the completeness, accuracy, or reliability of the study data. Santen's study team will review all protocol deviations and determine the list of significant protocol deviations prior to database lock. All enrolled subjects with any significant protocol deviation(s) will be tabulated by deviation category. In addition, two listings will be provided: (1) all significant protocol deviations and (2) subjects excluded from the per protocol population.

7.5. Impact of the COVID-19 Pandemic

The impact of the COVID-19 pandemic is defined as any disruption to the study and subject participation, such as changes in study visits, missed visits, subject discontinuations, etc. All

Safety Population subjects who experienced any of such impact will be summarized and listed along with the description of how their participation was altered.

7.6. **Prior and Concomitant Medications**

Non-study medications will be categorized into prior medications and concomitant medications. Specifically, *prior medication* is defined as any non-study medication taken and ended prior to the first administration of study treatment. *Concomitant medication* for an analysis period is defined as any non-study medication taken concurrently with the study medication during that analysis period.

For this study, non-study medications, including prior and concomitant medications, will be coded using World Health Organization (WHO) Drug Global, Version September 2018, format B3. Each non-study medication will be classified using the Anatomical-Therapeutic-Chemical (ATC) classification system and mapped to a WHO Drug preferred drug name.

Non-study medications will be summarized for the Safety population. Subjects taking any prior medications, will be tabulated by ATC level 3, level 4, and preferred drug name. A subject will be counted at most once for each prior medication, even if the subject took the same prior medication on multiple occasions. Subjects taking any concomitant medications will be tabulated similarly. In addition, prior medications and concomitant medications will also be listed, separately.

7.7. Treatment Compliance

Treatment compliance will be summarized only for the Double-Masked analysis period. For each subject in the Full Analysis Set (FAS), the treatment compliance at Day 1, Month 2, and Month 4 will be considered achieved if: 1) subject received an administration of study medication in the study eye ('Yes' to the eCRF question "Has the study eye been injected?"), and 2) the dose actually received was the planned dose. A subject will be considered fully compliant with double-masked treatment if the treatment compliance was achieved at all scheduled injection visits, up to Month 4 or Study Exit, which ever came earlier.

The treatment compliance will be summarized for the FAS population by planned Double-Masked treatment and overall. The treatment compliance statuses will also be listed by planned Double-Masked treatment, subject ID, and visit.

7.8. Treatment Exposure

The treatment exposure to DE-109 will be reflected by the number of injections received. The treatment exposure to Sham will be the number of administered Sham procedures. For the Double-Masked analysis period, Safety Population study eyes will be tabulated by the number of injections (1, 2, and 3) for each actual Double-Masked treatment and overall. The numbers of injections received during the Double-Masked, Open-Label, and the Entire Study analysis periods will also be listed for the Safety Population.

8. EFFICACY ANALYSES

8.1. Efficacy-Related Definitions

8.1.1. Study Eye and Fellow Eye

The *study eye* of a treated subject will be the eye that received an investigational product (IP) at baseline (Day 1). For subjects who enrolled both eyes in the study and both eyes received IPs at baseline (Day 1), both of their eyes will be considered as study eyes. Number of enrolled study eyes for each subject is defined as the number of eyes that received an IP administration at baseline (Day 1).

For subjects who enrolled one eye in the study, the other eye which did not receive an IP at baseline (Day 1) will be the non-study eye, or *fellow eye*. In a case when a subject enrolled in the study with both eyes eligible but only one of his/her eyes received an IP during the Double-Masked period, the eye which received an IP will be considered study eye, the eye which did not received any IPs will be considered fellow eye.

